2.7 Observation Indicators and Follow-up Plan

Observation indicators include cardiopulmonary interaction parameters and relevant biomarkers in clinical blood samples. The follow-up plan involves assessing patients within seven days after surgery to collect information on their recovery and test results.

2.8 Statistical Analysis Methods

Data will be analyzed using R or SPSS, with analyses including descriptive statistics, correlation analysis, and regression analysis.

3. Flowchart

4. Evaluation Criteria

Primary outcome measure: Incidence of ALI within 7 postoperative days.

ALI diagnosis currently uses the Berlin definition of acute respiratory distress syndrome (ARDS):

- Onset: Acute occurrence within one week of known injury or new/worsening respiratory symptoms;
- Chest imaging (X-ray or CT): Bilateral pulmonary opacities not fully explained by effusion, atelectasis, or nodules;
- Pulmonary edema cause: Respiratory failure not fully attributed to heart failure or fluid overload; if no related risk factors, objective tests (like Doppler echocardiography) are needed to exclude hydrostatic pulmonary edema;
- Oxygenation:

Mild: With CPAP/PEEP >5 cmH₂O, 200 mmHg <PaO₂ /FiO₂ <300 mmHg;

Moderate: With CPAP/PEEP >5 cmH₂O, 100 mmHg <PaO₂ /FiO₂ <200 mmHg;

Severe: With CPAP/PEEP >5 cmH₂O, PaO₂ /FiO₂ <100 mmHg. Opportunities for improved clinical trial designs in acute respiratory distress syndrome Wick, Katherine D et al.

The Lancet Respiratory Medicine, Volume 10, Issue 9, 916 – 924

Secondary outcome indicators include postoperative recovery status, hospitalization duration, and complication incidence, among others.

5. Safety Reporting and Adverse Event Management

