2.2 Study Population

Inclusion criteria: Patients aged ≥ 18 years undergoing major liver surgery (e.g., resection of two or more liver segments, liver transplantation). Exclusion criteria: Patients declining participation, having comorbidities affecting outcome assessment, or having incomplete data records.

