2.3 Sample Size and Calculation

This study will enroll 2,497 patients to ensure adequate statistical power for external model validation. In major liver surgery, ALI incidence is approximately 4.1%.

Performance Indicator	Hypothetical Value	Target 95% Confidence Interval Width (Corresponding Standard Error)	Sample Size: Number of Study Participants (Events) Required
-----------------------	--------------------	---	---

O/E	1	1 (0.245a)	390 (16)
Calibration Slope	1	0.2 (0.051)	2497 (103)
C-index	0.8	0.1 (0.0255)	1912 (79)
Standardized Net Benefit	0.53	0.2 (0.051)	2403 (99)

Assuming the linear predictor follows a skewed normal distribution, with an outcome event rate of 0.041. The required sample sizes, based on different model performance metrics, are shown above.

In summary, the minimum clinical sample size required for external model validation is 2,497 participants.

2.4 Inclusion Criteria:

- a. Aged ≥ 18 years; b. Scheduled for major liver surgery (e.g., resection of two or more liver segments, liver transplantation); c. Willing to participate and sign the informed consent form.

2.5 Exclusion Criteria:

- a. Patient refusal;
- b. Presence of comorbidities that may affect outcome assessment; c
- c. Incomplete recording of outcome measures;
- d. Failure to follow up postoperatively;
- e. Treating physician's judgment that the patient is unsuitable for inclusion;
- f. Participation in another study that may interfere with outcome assessment of this study.

2.6 Intervention Methods:

This study involves no therapeutic interventions for participants; only their clinical data and samples will be collected.

[figure not shown]

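### Does a P/F ratio of exactly 100 or 200 drop out of the primary outcome because the severity grades use strict signs?

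*Protocol*

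**What the plan says.** Section 4 (Evaluation Criteria) of the protocol sets the outcome as "Primary outcome measure: Incidence of ALI within 7 postoperative days" and names its standard: "ALI diagnosis currently uses the Berlin definition of acute respiratory distress syndrome (ARDS". It lists onset, imaging and oedema criteria, and then gives oxygenation only as three grades:

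- The first grade is printed as "Mild: With CPAP/PEEP >5 cmH₂O, 200 mmHg <PaO₂ /FiO₂ <300 mmHg", with both ends strict.
- The second grade is printed as "Moderate: With CPAP/PEEP >5 cmH₂O, 100 mmHg <PaO₂ /FiO₂ <200 mmHg", again with both ends strict.
- The third grade is printed as "Severe: With CPAP/PEEP >5 cmH₂O, PaO₂ /FiO₂ <100 mmHg", with its single bound strict.

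No overall P/F cut-off is stated apart from the grades, and no other section of the protocol returns to them. Section 2.3 sizes the validation cohort from a single ALI rate, "with an outcome event rate of 0.041". It requires 2,497 participants with 103 events, and the calibration slope is the measure that sets this number.

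**The concern.** The three grades are the whole oxygenation criterion, so a patient has to fall in one of them to count as ALI. With strict signs throughout, the mild and moderate grades both stop short of 200, and the moderate and severe grades both stop short of 100. A literal program would return no ALI at these two values and ALI on either side of them.

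This matters in principle because the rule labels the outcome in both phases: the retrospective data on which the models are built and the prospective cohort in which they are validated. If one coder followed the printed signs and another followed the named definition, the same reading could be labelled differently. Round ratios do occur in practice, because PaO₂ and FiO₂ are both recorded on coarse scales.

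**Working it through.** **1. The rule as printed.** Coding the three grades literally, with the other criteria met, gives:

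| P/F | Grade |
|---|---|
| 99.9 | severe |
| 100 | none |
| 100.1 | moderate |
| 199.9 | moderate |
| 200 | none |
| 200.1 | mild |
| 299.9 | mild |
| 300 | none |

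The gaps are two isolated values inside the range. The value 300 is the outer edge of the range and leaves no gap between qualifying values. The same holds for a CPAP/PEEP of exactly 5. The documents give no basis for judging either edge.

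**2. Whether the signs can be trusted.** The oxygenation block prints eight comparison signs, three for CPAP/PEEP and five for P/F, and all eight are strict. That pattern fits strict typing in the source, and it fits equally well a reading that lost the bar under each sign. A greater-or-equal sign does survive elsewhere, in section 2.2 ("Patients aged ≥ 18 years undergoing major liver surgery") and section 2.4 ("Aged ≥ 18 years"). It is a different sign in different sections, however, and a less-or-equal sign appears nowhere in the text to test the reading. The text cannot settle the point.

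**3. Where the grades are used.** The primary outcome in section 4 is binary, the models in section 1.2.1 predict ALI, and the sample size in section 2.3 uses one ALI rate. No section analyses mild, moderate and severe ALI separately.

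**4. How much could be at stake.** The plan has no figure for this. Its event count is reproduced first: 2,497 × 0.041 = 102.4, printed as 103. The share of qualifying readings that lie exactly on 100 or 200 has to be assumed.

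For illustration, take FiO₂ from 0.30 to 1.00 in steps of 0.05 (15 values), PaO₂ in whole mmHg from 40 upward, P/F below 300, and all combinations equally likely.

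- Combinations: the sum of (300 × FiO₂ − 40) over the 15 values = 300 × 9.75 − 15 × 40 = 2,325.
- Exactly 100: PaO₂ = 100 × FiO₂, which is at least 40 for 13 of the 15 values.
- Exactly 200: PaO₂ = 200 × FiO₂, which is at least 40 for all 15 values.
- Share: 28/2,325 = 1.20%, and 103 × 28/2,325 = 1.24 events.

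Other PaO₂ floors change little: 27/2,310 with 41, 26/2,175 with 50 and 24/2,025 with 60, each about 1.2%. Recording precision changes a great deal. With PaO₂ to 0.1 mmHg and a floor of 40, the share is 28/23,250 = 0.12%, or about 0.12 events. A wider assumed share of 0.2% to 3% gives 103 × 0.002 = 0.2 to 103 × 0.03 = 3.1 events.

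**5. Effect on precision.** The plan's standard error of 0.051 for the calibration slope gives a width of 2 × 1.96 × 0.051 = 0.200. If the standard error scales with 1/√events and 1.24 events were lost, it becomes 0.051 × √(103/101.76) = 0.0513, with a width of 0.201. If 3.09 were lost, it becomes 0.051 × √(103/99.91) = 0.0518, with a width of 0.203. These are per-reading shares applied as if each patient had one reading. A patient with any other qualifying reading off the boundary within seven days still counts, so the loss per patient would be smaller than the share assumed.

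**The case for a change.** The strongest case for acting is that the protocol itself writes out the diagnostic rule for its primary outcome, so this is not a detail left to an analysis plan. The defect can be seen without any outside source, because a ratio between two qualifying ratios does not itself qualify. A clinician would look past the signs, but code in R or SPSS that copies them would not. Correcting the line would cost almost nothing before prospective enrolment proceeds.

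The logical point stands for the text as shown. What does not stand is the step from there to a fault in the plan. It is not known that the source has strict signs. The protocol also already supplies the tie-breaker, since it names the definition that the three lines summarise. And to treat the boundary between two adjacent grades of ALI as absence of ALI is a reading that no one labelling these patients is likely to intend.

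**Conclusion.** The concern does not call for a change. As shown, exactly 100 and exactly 200 fall in no printed grade. This is at most a clerical matter of signs, and it may be no more than a loss in reading the PDF. The gap affects which severity label a patient gets more than whether the patient has ALI, and only the latter is analysed. Analysts would fill it by counting the value as ALI and would consult the named definition for the grade.

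The effect on the outcome cannot be estimated from the documents. The illustrations above, from about 0.1 to 3 of 103 events, rest entirely on assumed recording precision, equally likely combinations or an assumed share. They show only that the answer depends on those assumptions and is small throughout. None of them alters the sample size of 2,497 or any conclusion of the study. Anyone with the source file can check the signs in passing. If they prove strict there, the sponsor can reconcile the grade boundaries with the definition it names as an editorial matter.

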5.1 Definitions of Adverse Events and Serious Adverse Events

An adverse event (AE) is any unfavorable event occurring during the study that may impact the participant's well-being. A serious adverse event (SAE) refers to an event that results in death, is life-threatening, requires hospitalization or prolongs hospital stay, causes permanent or significant disability/damage, or leads to congenital anomalies/birth defects.

5.2 Management of AEs and SAEs

AEs will be promptly assessed and treated, with treatment plans adjusted if necessary. For SAEs, immediate emergency measures will be taken to ensure participant safety, and they will be reported to the ethics committee without delay.

5.3 Reporting Procedure

AEs and SAEs will be reported in accordance with hospital regulations and the requirements of the ethics committee.

6. Medical Ethics Risk Analysis

Ethical Issues: This study involves privacy protection and informed consent of participants.

Countermeasures: We will strictly adhere to ethical principles to ensure participant privacy and informed consent rights. Personal information and samples will be anonymized to

safeguard privacy. Throughout the study, we will fully respect participants' autonomy and voluntary participation.
